13.2. Data Quality Control

Data Management is responsible for the accuracy, quality, completeness, and internal consistency of the data from this study. Data handling, including data quality control, will comply with international regulatory guidelines, including ICH GCP guidelines. Data management and control processes specific to this study, along with all steps and actions taken regarding data management and data quality control, will be described in a data management plan.

Case report forms received will be processed and reviewed for completeness, consistency, and the presence of mandatory values. Applicable terms will be coded according to the coding conventions for this study. Logical checks will be implemented to ensure data quality and accuracy. Any necessary changes will be made in the clinical database, and data review and validation procedures will be repeated as needed. Data from external sources will be compared with the information available in the CDMS. Discrepancies found will be queried.

Data corrections in the CDMS will be made using the CDMS update function. The system requires a reason for each change and keeps a complete audit trail of the data values, dates, and times of modifications, and authorized electronic approvals of the changes.

At the conclusion of the study, the CDMS and all other study data will be locked to further additions or corrections. Locking the study data represents the acknowledgement that all data have been captured and confirmed as accurate.

13.3. Archiving of Case Report Forms and Source Documents

13.3.1. Sponsor Responsibilities

The sponsor will have final responsibility for the processing and quality control of the data. Data management oversight will be carried out as described in the sponsor's SOPs for clinical studies.

Day to day data management tasks for this study are delegated to a contract organization, and these functions may be carried out as described in the SOPs for clinical studies at that organization. These SOPs will be reviewed by the sponsor before the start of data management activities. The original CRFs will be archived by the sponsor. Investigational center-specific CRFs will be provided to the respective investigational centers for archiving.

13.3.2. Investigator Responsibilities

The investigator must maintain all written and electronic records, accounts, notes, reports, and data related to the study and any additional records required to be maintained under country, state/province, or national and local laws, including, but not limited to:

- full case histories
- signed informed consent forms
- patient identification lists
- case report forms for each patient on a per-visit basis
- data from other sources (eg, central laboratory, bioanalytical laboratory, central image center, electronic diary)
- safety reports
- financial disclosure reports/forms
- reports of receipt, use, and disposition of the study drug
- copies of all correspondence with sponsor, the IEC/IRB, and any competent authority

The investigator will retain all records related to the study and any additional records required, as indicated by the protocol and according to applicable laws and regulations, until the CRO or sponsor notifies the institution in writing that records may be destroyed. If, after 25 years from study completion, or earlier in the case of the investigational center closing or going out of business, the investigator reasonably determines that study record retention has become unduly burdensome, and sponsor has not provided written notification of destruction, then the investigator may submit a written request to sponsor at least 60 days before any planned disposition of study records. After receipt of such request, the sponsor may make arrangements

for appropriate archival or disposition, including requiring that the investigator deliver such records to the sponsor. The investigator shall notify the sponsor of any accidental loss or destruction of study records.

14. FINANCING AND INSURANCE

A separate clinical study agreement, including a study budget, will be signed between each principal investigator and the sponsor (or the CRO designated by the sponsor) before the study drug is delivered.

This clinical study is insured in accordance with applicable legal provisions. The policy coverage is subject to the full policy terms, conditions, extensions, and exclusions. Excluded from the insurance coverage are *inter alia*, damages to health, and worsening of previous existing disease that would have occurred or continued if the patient had not taken part in the clinical study.

The policy of Clinical Trials Insurance will be provided to the investigational centers by the sponsor.

For covered clinical studies (see 21CFR54), the investigator will provide the sponsor with financial information required to complete FDA 3454 form. Each investigator will notify the sponsor of any relevant changes during the conduct of the study and for 1 year after the study has been completed.

15. REPORTING AND PUBLICATION OF RESULTS

The sponsor is responsible for ensuring that the public has access to the appropriate information about the study by conforming to national, local, and regional requirements and regulations for registration and posting of results.

The sponsor is responsible for the preparation of a CSR, in cooperation with the principal investigator. The final report is signed by the sponsor and, if applicable, by the principal investigator.

When the sponsor generates reports from the data collected in this study for presentation to competent authorities, drafts may be circulated to the principal investigator for comments and suggestions. An endorsement of the final report will be sought from the principal investigator.

All unpublished information given to the investigator by the sponsor shall not be published or disclosed to a third party without the prior written consent of the sponsor. The primary publication from this study will report the results of the study in accordance with the “Recommendations for the Conduct, Reporting, Editing, and Publication of Scholarly Work in Medical Journals” (www.ICMJE.org). Publication of the results will occur in a timely manner according to applicable regulations. Authorship will be based on meeting all the following 4 criteria:

- substantial contributions to the conception or design of the work; or the acquisition, analysis, or interpretation of data for the work
- drafting the work or revising it critically for important intellectual content
- final approval of the version to be published
- agreement to be accountable for all aspects of the work in ensuring that questions related to the accuracy or integrity of any part of the work are appropriately investigated and resolved

The publications committee established by the sponsor will oversee this process. Additional publications may follow. Policies regarding the publication of the study results are defined in the financial agreement.

No patent applications based on the results of the study may be made by the investigator nor may assistance be given to any third party to make such an application without the written authorization of the sponsor.

APPENDIX A. ASTHMA CONTROL QUESTIONNAIRE

(Sample provided in this appendix is for reference only.)

[figure not shown]

[figure not shown]

[figure not shown]
Source: Juniper EF, O'Byrne PM, Guyatt GH, Ferrie PJ, King DR. Development and validation of a questionnaire to measure asthma control. Eur Respir J 1999;14:902-7.

[figure not shown]
APPENDIX B. ASTHMA QUALITY OF LIFE QUESTIONNAIRE

[figure not shown]
(Sample provided in this appendix is for reference only.)

[figure not shown]

Source: Juniper EF, Guyatt GH, Epstein RS, Ferrie PJ, Jaeschke R, Hiller TK. Evaluation of impairment of health-related quality of life in asthma: development of a questionnaire for use in clinical trials. *Thorax* 1992;47:76-83.

APPENDIX C. CLINICAL CRITERIA FOR DIAGNOSING ANAPHYLAXIS

Anaphylaxis is highly likely when the following criteria are fulfilled:

Acute onset of an illness (minutes to several hours) with involvement of the skin, mucosal tissue, or both (eg, generalized hives, pruritus or flushing, swollen lips tongue-uvula) AND AT LEAST ONE OF THE FOLLOWING:

- Respiratory compromise (eg, dyspnea, wheeze-bronchospasm, stridor, reduced peak expiratory flow [PEF], hypoxemia)
- Reduced blood pressure (BP) or associated symptoms of end-organ dysfunction (eg, hypotonia [collapse], syncope, incontinence)

Source: Modified from Sampson HA, Munoz-Furlong A, Campbell RL, Adkinson NF, Jr., Bock SA, Branum A, et al. Second symposium on the definition and management of anaphylaxis: summary report—Second National Institute of Allergy and Infectious Disease/Food Allergy and Anaphylaxis Network symposium [reprint in Ann Emerg Med 2006;47(4):373-80; PMID: 16546624]. J Allergy Clin Immunol 2006;117(2):391-7.

**LIST OF ABBREVIATIONS AND DEFINITIONS OF TERMS**

Abbreviation	Term
AQLQ	Asthma Quality of Life Questionnaire
BMI	Body mass index
CRF	Case report form
CTCAE	Common Terminology Criteria for Adverse Events
DPP4	Dipeptidyl peptidase 4
ECG	Electrocardiogram/Electrocardiography
FEF	Forced Expiratory Flow
FeNO	Fractional exhaled Nitric Oxide
FEV	Forced Expiratory Volume
FDG	Fludeoxyglucose F 18
FVC	Forced Vital Capacity
GLG	Global Lung Glycolysis
HC	Healthy control
IgE	Immunoglobulin E
ITT	Intent-to-Treat
LP	Lung Parenchyma
MedDRA	Medical Dictionary for Regulatory Activities
PCSA	Potentially clinically significant abnormal
PEFR	Peak Expiratory Flow Rate
PET/CT	Positron Emission Tomography/Computed Tomography
PP	Per-Protocol
R&D	Research and Development
SD	Standard Deviation
SE	Standard Error
SI	Standard International
SOC	System Organ Class
SOP	Standard Operating Procedure
TARC	Thymus and Activation Regulated Chemokine

## INTRODUCTION

This Statistical Analysis Plan describes the planned analysis and reporting for Teva Branded Pharmaceutical Products R&D, Inc study CEP38072-AS-40105, (Distribution of Eosinophils in Asthma after Reslizumab (DEAR). A 7-week, Placebo-Controlled, Double-Blinded, Parallel-Group, Imaging Study Using Positron Emission Tomography/Computed Tomography (PET/CT) to Characterize the Effect of Intravenous Reslizumab on Airway Inflammation in Patients with Eosinophilic Asthma), and was written in accordance with SOP GBP\_RD\_702 (Statistical Analysis Plan).

The reader of this Statistical Analysis Plan is encouraged to read the study protocol for details on the conduct of this study, the operational aspects and times of clinical assessments, and the timing for completing the participation of a patient in this study.

The SAP is intended to be in agreement with the protocol, especially with regards to the primary and all secondary endpoints and their respective analyses. However, the SAP may contain more details regarding these particular points of interest, or other types of analyses (e.g. other endpoints). When differences exist in descriptions or explanations provided in the study protocol and this Statistical Analysis Plan, the Statistical Analysis Plan prevails; the differences will be explained in the Clinical Study Report.

## 1. STUDY OBJECTIVES AND ENDPOINTS

### 1.1. Primary and Secondary Study Objectives and Endpoints

#### 1.1.1 Primary Objectives and endpoints

This study is designed in two parts: Part 1 is validation of PET/CT scan and Part 2 is evaluation of the effect of reslizumab on inflammation in the lungs. There are 2 related primary objectives of this study:

- To establish that positron emission tomography (PET)/computerized tomography (CT) imaging of the lung can reliably distinguish healthy control (HC), non-asthmatic subjects and patients with severe asthma with an eosinophilic phenotype (Part 1: initial validation of PET/CT scan).
- If the utility of PET/CT scanning is established as per objective 1 (Part 1): Part 2 objective is to show that reslizumab produces a reduction in signal intensity (reduction in lung inflammation) in patients with severe asthma with an eosinophilic phenotype (Part 2: evaluation of the effect of reslizumab vs placebo in reducing inflammation).

For primary objective 1 (Part 1), a  $\leq 10\%$  variability between the first and second measurements of PET/CT scans as measured by global lung glycolysis (GLG) within each group [HCs (n=5) and patients with asthma (n=10)] will be considered as the maximum allowed variability. This criterion is a measure of intra-group reproducibility. At this point (i.e. establishing intra-group reproducibility), healthy subjects are considered completed.

A  $\geq 5\%$  difference in GLG between HC subjects and patients with eosinophilic asthma, based on the average of the 2 measurements of PET/CT, will be selected as minimal difference that validates the ability PET/CT to differentiate these 2 populations of study participants. This criterion is a measure of inter-group reproducibility.

Only after these intra- and inter-group variability criteria of Part 1 are met, the patients with asthma will be considered eligible to enter Part 2 of the study and randomly assigned in double-blind fashion to receive either placebo (n=5) or reslizumab (n=5). If these exploratory criteria (Part 1) are not met (8 or more asthma patients do not meet the criteria to enter Part 2 of the protocol), the study will be reevaluated.

For primary objective 2 (Part 2), the primary efficacy endpoint is the change from baseline to week 4 in global lung glycolysis (GLG) (i.e.,  $\Delta$ GLG).

The supportive primary efficacy endpoint is the change from baseline to week 4 in lung parenchyma (LP) standardized uptake value (SUV) mean.

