- If the utility of PET/CT scanning is established as per objective 1: to show that reslizumab produces a reduction in signal intensity (reduction in lung inflammation) in patients with severe asthma with an eosinophilic phenotype.

Secondary Objectives: The secondary objectives of this study are:

- to demonstrate a correlation between the benefit observed on imaging (PET/CT) with:
 - reductions blood eosinophil counts
 - improvement in clinic visit lung function
 - reductions in fractional exhaled nitric oxide (FeNO)

- improvements in Asthma Quality of Life questionnaire (AQLQ) scores

Exploratory Objectives: The exploratory and other objectives of the study are:

- to demonstrate a correlation between changes in the lung PET/CT signal produced by reslizumab and serum biological markers of asthmatic inflammation
- to demonstrate a correlation between changes in the lung PET/CT signal produced by reslizumab and other lung function variables including forced vital capacity (FVC), peak expiratory flow rate (PEFR) and forced expiratory flow at the 25% point to the 75% point of forced vital capacity (FEF_{25%-75%})
- to demonstrate that reslizumab produces greater reductions in inflammation of whole body lymph nodes and bone marrow than placebo as seen on PET/CT
- for those patients that can produce sputum, to demonstrate an association between changes in sputum eosinophil numbers produced by reslizumab and the lung PET/CT signal produced by reslizumab

Study Endpoints:

This study is designed in 2 parts. Part 1 is a validation step which will include 2 measures, (1) the intrapatient reproducibility in the global lung glycolysis (GLG) measure, and (2) the signal window representing difference in the measure of GLG for individual patients with severe asthma with an eosinophilic phenotype and the mean GLG of the healthy controls group. The limit for step 1 above (reproducibility within patients) will be set at $\leq 10\%$ of sequential GLG measures. The limit for step 2 above (the signal window) will be set at $\geq 5\%$. These limits have been provided by subject matter experts.

Primary Endpoint: The primary efficacy endpoint is the change from baseline to week 4 in GLG (Δ GLG).

The supportive primary efficacy endpoint is the change from baseline to week 4 in lung parenchyma (LP) standardized uptake value (SUV) mean.

Secondary Endpoints: The secondary efficacy endpoints are:

- the change from baseline to week 4 in blood eosinophil counts

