Part 2 will be a 7-week double-blind evaluation of patients with severe asthma with an eosinophilic phenotype that have been randomized to receive a single dose of either placebo or reslizumab at 3 mg/kg.

Part 1

Within 7 days (±3 days) of eligibility being confirmed, participants will have a PET/CT scan as per the PET/CT scan protocol described in Part 2 below. Participants will return to the [REDACTED] [REDACTED] 7 days (±3) after the first PET/CT scan (taken during visit 2) for a second PET/CT scan following the same procedures described above. HC subjects (n=5) may also have a second sputum induction and blood sample collection at [REDACTED] with 1 day of the 2nd PET/CT scan, if feasible (preferred but not required). Healthy subjects will be considered

complete at this time. Only after all 5 HCs have completed the study will patients with asthma be screened.

If the relative difference in GLG (based on the average of the 2 measurements) between healthy and asthma patients will be $\geq 5\%$, then the asthma patients will be randomized.

A 10% variability (measured as relative difference between first measurement and second measurement) between PET/CT scans as measured by GLG within each group will be considered as the maximum allowed variability. The part 1 criteria have been set at these levels to observe a difference between the healthy subjects and patients with asthma and to ensure intra-group reproducibility; the criteria are based on the investigators' prior experience. If these exploratory criteria are not met (eg, 8 or more patients do not meet the criteria to enter Part 2 [inclusion criteria k and l]), then the study will be reevaluated.

Part 2

If eligible (eg, if inter- and intra-group GLG variability criteria are met), patients will be randomized. This may occur at any time after confirmation of eligibility and up to the time of dosing. Patients will return to [REDACTED] for baseline clinical, serological, and biochemical measures at the Clinical Research Center (CRC) according to standard procedures. Once these are completed, patients will receive either placebo or reslizumab and will receive the infusion at [REDACTED]. Any new serious adverse events, reslizumab-related adverse events, and new concomitant medications will be reported.

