4.1. Patient Inclusion Criteria

Healthy subjects and patients may be enrolled in this study only if they meet all of the following criteria:

- a. Male or female, 18 through 50 years of age.
- b. Females that are either surgically sterile, are 2 years postmenopausal, or have a negative pregnancy test beta-human chorionic gonadotropin at screening (serum) and all PET/CT imaging visits (urine).
- c. Females of childbearing potential (not surgically sterile or 2 years postmenopausal), have to use a medically accepted method of contraception and have to agree to continue to use of this method for the duration of the study and for 5 months after study drug administration. Acceptable methods of contraception include barrier method with spermicide, abstinence, intrauterine device (IUD), or steroid contraceptive (oral, transdermal, implanted, and injected). Note: partner sterility alone is not acceptable for inclusion in the study.
- d. Subjects and patients with less than 10-pack year history of smoking.

Patients may be included in the study only if they also meet all of the following, additional criteria:

- e. Male or female, 18 through 50 years of age, with a previous diagnosis of asthma.
- f. Patients taking inhaled fluticasone at a dosage of at least 440 mcg daily, or equivalent.
- g. The patient's baseline asthma therapy regimen (including, but not limited to, inhaled corticosteroids, leukotriene receptor antagonists, 5-lipoxygenase inhibitors, or cromolyn) must be stable for 30 days prior to screening and judged by their treating physician to be able to continue without dosage changes throughout the study.
- h. Patients with a blood eosinophil level of at least 400/ μ L at screening. Patients with a blood eosinophil level below 400/ μ L will be given 2 additional screening opportunities to determine blood eosinophil levels.
 - i. Patients with airway reversibility of at least 12% to β -agonist administration.
 - j. Patients with an ACQ score of at least 1.5 at either screening or baseline visits.

Patients may be included in Part 2 of the study only if they also meet the following, additional criteria:

- k. the intrapatient reproducibility, taken as sequential GLG measures on visits 2 and 3 (Table 2), differs by only $\leq 10\%$

1. the intragroup variability (signal window), taken as a difference in the 2 subcriteria (below) to be $\geq 5\%$:

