Relative differences between the first (V2) and second (V3) measurements will be summarized, by total/regional lung and patients/HC group, using descriptive summary statistics, based on enrolled analysis set (Summary 15.2.1.1).

Variability between HC group and individual patients with eosinophilic asthma (Part 1):

The planned method to assess whether the difference in GLG measure between HC subjects, as a group, and individual patients (one-by-one) with eosinophilic asthma is  $\geq 5\%$  will be calculated as follows:

- For Females: Relative difference of GLG =  $(GLG6i-GLG5f)/GLG5f$ , i.e., difference in GLG (based on average of 2 measurements) between each individual patient with asthma and the mean of HC group, for females.
- For Males: Relative difference of GLG =  $(GLG6i-GLG5m)/GLG5m$ , i.e., difference in GLG (based on average of 2 measurements) between each individual patient with asthma and the mean of HC group, for males.

5=average of 2 GLG measurements (1 and 2) of all HCs by sex

6=average 2 GLG measurements (3 and 4) for each individual asthma patients

GLG6i will be calculated for each individual male/female patient using his/her two GLG measurements at V2 and V3 (Part 1). If this amount is  $\geq 5\%$  then the patient will be randomized.

Relative differences in GLG measures between the HC group and individual patients with asthma will be summarized for each sex, by total lung/regional lung, using descriptive summary statistics, based on enrolled analysis set (Summaries 15.2.1.2 and 15.2.1.3).

Relative change from baseline to week X in GLG ( $\Delta$ GLG) (Part 2):

$\Delta$ GLG =  $(GLGwX - GLG_{baseline})/GLG_{baseline}$

wX= post-randomization week (week 2 /V5, week 4/V6, and week 6/V7).

GLG Baseline= the average of two measurements at Visits 2 and 3 of Part 1 (see section 4.2 of the SAP).

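### The 10% limit on GLG reproducibility is stated both per individual and per group, no group statistic is named, and the planned summary of signed differences does not show whether the limit is met

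*SAP*

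**What the plan says.** **Per individual.** The Protocol Synopsis (Study Endpoints) says "The limit for step 1 above (reproducibility within patients) will be set at" 10% or less. Criterion k in Protocol 4.1 requires that "the intrapatient reproducibility, taken as sequential GLG measures on visits 2 and 3 (Table 2), differs by only" 10% or less. Footnote k to Protocol Table 2 and to SAP Table 1 qualifies patients one at a time. SAP 2.1 speaks of reproducibility within patients. SAP 6.2.1 heads its calculation as intra-subject and defines the Part 1 endpoint as intra-patient variability in each group.

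**Per group.** Protocol 3.1 says that a 10% variability "between PET/CT scans as measured by GLG within each group will be considered as the maximum allowed variability". The Synopsis and Protocol 6.1.3 also tie the limit to each group. SAP 1.1.1 says that 10% "within each group [HCs (n=5) and patients with asthma (n=10)] will be considered as the maximum allowed variability" and adds: "This criterion is a measure of intra-group reproducibility". SAP 2.1 and 6.2.1 repeat the group form.

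**Formula.** Protocol 6.1.3 and SAP 6.2.1 define the difference as (second scan − first scan)/first scan, with no absolute value.

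**Output.** SAP 6.2.1 plans: "Relative differences between the first (V2) and second (V3) measurements will be summarized, by total/regional lung and patients/HC group, using descriptive summary statistics". This is Summary 15.2.1.1, on the enrolled analysis set. SAP 4.1 defines descriptive statistics as n, mean, SD, median, minimum and maximum. SAP 6.2.2 also lists the Part 1 variability data and the variables behind them.

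**Consequence.** Under SAP 1.1.1 and 2.1 the study is re-evaluated if 8 or more asthma patients fail the criteria for Part 2. Protocol 3.1 gives the same count as an example.

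**The concern.** Reproducibility is one of the two validation measures in Part 1, and primary objective 2 depends on objective 1. A limit meant for one person's pair of scans is a different requirement from a limit on a group summary. If the unit and the statistic are not fixed in advance, the same data can support opposite answers, and the choice could be made with the data in view.

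The healthy controls are the most exposed. Criterion k applies only to patients entering Part 2, so for the controls the group form is the only explicit rule, and nothing says what follows if a control exceeds 10%. Yet their scan averages form the reference for the 5% signal window. Protocol 6.1.3 and SAP 6.2.1 compute that reference separately for women and men. With 2 to 3 women among five controls (Protocol 1.7), each reference rests on 2 or 3 people.

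**Working it through.** The plan gives no SD, CV or operating characteristic for the 10% limit, so there is no figure to reproduce.

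**1. Is one unit fixed?** No. Each document contains both forms. The SAP introduction says the SAP prevails where the two differ, but that cannot settle a conflict inside the SAP itself.

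**2. Which group quantity is compared with 10%?** None is named. Mean, median, maximum and share of participants within 10% are all possible.

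**3. What do the planned mean and median show?** The difference is signed, so opposite errors cancel. Take five invented control differences: +30%, −30%, +25%, −25% and 0%.
- Mean = 0 and median = 0, but 4 of 5 are outside 10%.
- SD = √[(2×0.30² + 2×0.25²)/4] = √0.07625 = 27.6%; minimum −30%, maximum +30%.
- Within-subject CV, as the square root of half the mean squared difference: √[(0.305/5)/2] = 17.5%.

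The mean and median look perfect. The SD and range in the same table reveal the problem, but the plan does not say which of them decides.

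**4. How far apart can the readings be?** Assumptions: independent scans, no systematic shift, and a within-subject CV of 5% to 20% (not in the documents). Normal approximation: the SD of one relative difference is s = √2×CV; P(one participant within 10%) = 2Φ(0.10/s) − 1; P(mean of n within ±10%) = 2Φ(0.10√n/s) − 1.

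At CV 10%, s = 0.141. One participant: 2Φ(0.707) − 1 = 0.52. Mean of five: 2Φ(1.581) − 1 = 0.89.

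A simulation with log-normal scan error (200,000 groups per setting) gave:

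| Assumed CV | One participant within 10% | All five controls within 10% | Mean of five within ±10% | Mean of ten within ±10% | Mean absolute difference of five ≤10% |
|---|---|---|---|---|---|
| 5% | 0.84 | 0.43 | 0.998 | 1.00 | 0.98 |
| 10% | 0.52 | 0.04 | 0.88 | 0.97 | 0.40 |
| 15% | 0.37 | 0.007 | 0.69 | 0.84 | 0.11 |
| 20% | 0.28 | 0.002 | 0.55 | 0.69 | 0.035 |

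The normal approximation for the mean of five at CV 15% is 0.71, so about 0.70 is a fair summary.

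**5. What does the re-evaluation trigger add?** Counting failures of criterion k alone among ten patients, P(8 or more fail) in the same simulation is 0.04 at CV 10%, 0.23 at 15% and 0.44 at 20%. It works on individuals, but it does not cover the controls.

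**The case against.** The case that this is only loose wording is strong. The SAP's phrase about intra-patient variability in each group suggests that the limit applies to individuals in both groups. Protocol 6.1.3 places its formula under an intra-patient heading and does not average over subjects. Where the SAP wants an average over controls, for the signal window, it says so. The only numerical study-level consequence counts individual patients. No passage compares a group mean with 10%. SD, minimum and maximum stand in the same summary: at CV 15%, 99% of simulated control groups whose mean is within 10% still show a value beyond 10% in the range. Individual values are listed, and the study is exploratory.

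The size also depends on the assumed CV and the assumed statistic. At CV 5% most individuals comply. A rule based on the mean absolute difference would usually reject a poor method: at CV 15% five controls would pass with probability 0.11 and ten patients with 0.035.

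All of this stands, and it limits the harm. But it shows which reading is likely, not which is specified. Visible spread does not define a pass, the label in SAP 1.1.1 remains explicitly intra-group, and no individual rule is written for the controls.

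**Conclusion.** The point holds as a gap in definition. The 10% limit has two units in both documents, no group statistic is tied to it, and the signed mean and median are unsuited to measuring repeatability. The exposure is mainly the reproducibility conclusion for objective 1 and the five controls behind the 5% signal window.

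A reader might infer three stronger things that the documents do not support:
- **That the SAP replaced a per-patient rule with a group rule.** It did not; SAP 2.1, footnote k to SAP Table 1 and SAP 6.2.1 keep the per-patient form.
- **That the planned output hides poor repeatability.** It does not; SD, range and listings would show it.
- **That a patient with poorly repeatable scans could enter Part 2 on a group pass.** Criterion k still applies to each patient, and Protocol 4 grants no prospective waivers.

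The probabilities illustrate what would follow if the signed group mean were used. They rest on an assumed CV, independent scans and no shift, and they say nothing about the actual repeatability of GLG.

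**What to change.** In SAP 1.1.1, 2.1 and 6.2.1 and Protocol 3.1 and 6.1.3, with the Synopsis to match, state the limit once: the absolute relative difference |V3 − V2|/V2 is at most 10% for each participant, controls and patients alike. The absolute value also closes a literal gap, since a large fall satisfies a signed limit of 10% or less. Say whether a control outside the limit stays in the reference mean.

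In Summary 15.2.1.1, add by group the number of participants within 10% and the within-subject CV, for example as the square root of half the mean squared relative difference. Both can be descriptive; an interval is optional. Keep the enrolled analysis set already planned, so that patients who fail criterion k are counted. State that the group mean or median of signed differences will not decide reproducibility.

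The cost is wording in two documents and an addition to one table, with no new data. The downside is that reported reproducibility may look less favourable.
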